## 2.0 Purpose

The purpose of this study is to evaluate the safety of Adcetris in patients with relapsed/refractory CD30+ Hodgkin's lymphoma or anaplastic large cell lymphoma in the routine clinical setting, as well as to collect efficacy information for reference.

## 3.0 Estimated Enrollment and Its Rationale

### 3.1 Estimated enrollment

140 patients (with relapsed/refractory CD30+ Hodgkin's lymphoma or anaplastic large cell lymphoma)

### 3.2 Rationale

It is expected that the detailed evaluation of peripheral nerve disorders, infections, neutropenia, infusion reactions, and pulmonary disorders will help better understand the safety profile of Adcetris in the routine clinical setting, which will lead to the assessment of the risk-benefit balance of the drug.

The frequencies of peripheral nerve disorders, infections, neutropenia ( $\geq$ Grade 3), infusion reaction, and pulmonary disorder in non-Japanese phase 2 studies (pooled study data from a study in patients with Hodgkin's lymphoma [SG035-0003, 102 patients] and a study in patients with systemic anaplastic large cell lymphoma [SG035-0004, 58 patients]) were 56%, 61%, 20%, 11%, and 6%, respectively.

Observation of infusion reactions with the lowest frequency of  $\geq 10$  patients, aside from pulmonary disorders, with a probability of 95% would require 140 patients, which was therefore determined to be the estimated enrollment. It is estimated that when the number of patients enrolled reaches 140 patients,  $\geq 4$  patients have adverse events of pulmonary disorder with a probability of 95%.

## 4.0 Eligible Patients

All patients receiving treatment with Adcetris

## 5.0 Dosage Regimen

The usual adult dosage is 1.8 mg/kg (body weight) of brentuximab vedotin (recombinant) infused intravenously once every three weeks. The dose should be adjusted depending on the patient's condition.

See the "PRECAUTIONS" section of the package insert.

## 6.0 Expected Study Institutions by Department

The study will be conducted at all institutions using Adcetris (e.g., department of hematology) (approximately 100 study institutions are expected to participate in the study).

## 7.0 Methods

### 7.1 Observation period

From the start of treatment with Adcetris until the completion of 16 cycles [3 weeks per cycle]

#### \* Rationale for the selection of the observation period

The assessment of the treatment cycle with the initial onset of adverse events in a clinical study [SGN35-006, the extended treatment group] evaluating the safety of Adcetris after Cycle 17 showed a tendency that most adverse events occurred before Cycle 16. In addition, the types and severities did not differ between adverse events occurring after Cycle 17 and those occurring before Cycle 16. This suggested that the safety profile of Adcetris would be generally determined before Cycle 16. Therefore, the observation period was defined as the period from the start of treatment with Adcetris until the completion of 16 cycles.

### 7.2 Request for participation in this study and contract with each study institution

Paper-based case report forms will be used. To ask each study institution to participate in the study, the medical representative of Takeda Pharmaceutical Company Limited (Takeda MR) will confirm before supply of Adcetris and the start of the study that each study institution meets all requirements for study institutions and investigators specified below, and have a written contract with the study institution after prior explanation of the study provided before supply of Adcetris.

#### (1) Requirements for each study institution and investigator

##### 1) Requirements for each study institution

[1] Is able to cooperate with this all-case surveillance and have a contract with the sponsor.

[2] Is able to provide specialized treatment for hematopoietic tumors.

[3] Is able to provide emergency treatment if required (including a case where such a treatment can be provided in conjunction with another institution

).

\* When emergency treatment is provided in conjunction with another institution, information on Adcetris safety measures and treatment of adverse drug reactions should be shared between the institution and the other institution to build a coalition.

2) Requirements for each investigator

[1] Has adequate knowledge and experience regarding the treatment of hematopoietic tumors, or is under the direction of a healthcare professional having such knowledge and experience.

[2] Is able to cooperate with this all-case surveillance.

(2) Prior explanation of the study to be provided before supply of Adcetris and the request for participation in this study

Using “Request for Participation in the Special Drug Use Surveillance,” “Study Outline,” “Patient Enrollment Form (sample),” “Case Report Form Parts 1 and 2 (sample),” “Precautions for Use/Instruction Manual,” and “Proper Usage Guide,” the Takeda MR will explain the purpose and methods (e.g., all-case surveillance) of this survey study and information regarding the proper use of Adcetris to the investigator and ask him/her to participate in the all-case surveillance.

The Takeda MR will also confirm with the investigator that the institution and the investigator meet all requirements.

(3) Request for participation in this study and contract with each study institution

The Takeda MR will have a written contract with the study institution after obtaining their agreement to participate in this study. Takeda Pharmaceutical Company Limited will inform the outsourced Adcetris supplier that the contract is concluded and Adcetris should be supplied to the study institution. The Takeda MR will deliver patient enrollment forms to the investigator.

7.3 Method of patient enrollment

The central enrollment method via FAX will be used. For each patient scheduled to receive treatment with Adcetris after the date of the start of the term of the contract with the study institution, the investigator will complete patient enrollment by submitting the Patient Enrollment Form with information required for patient enrollment filled in (see Section 9.1) via FAX to the Central Enrollment Center (see Section 12.3) until noon of the day before the date of the expected initial dose of Adcetris.

The Central Enrollment Center will review the Patient Enrollment Form and send the Enrollment Completion Notice to the investigator via FAX. After receiving the Enrollment Completion Notice, the investigator will initiate treatment with Adcetris.

The Case Report Form consists of Parts 1 and 2 per patient.

The Takeda MR will deliver Case Report Form Part 1, which is issued after enrollment confirmation by the Central Enrollment Center, to the investigator. Case Report Form Part 2 is issued after the completion of follow-up on Case Report Form Part 1.

#### 7.4 Completion and submission of the case report form

For all patients requiring the completion of the case report form, the investigator will complete the case report form during the period from the start of treatment with Adcetris until the end of Cycle 4 and within 1 month after the end of Cycle 16, and submit it to the Takeda MR.

If treatment with Adcetris is discontinued for any reason before the end of the observation period, the investigator will complete the case report form within 1 month after the completion of required observation submit it to the Takeda MR. If treatment with Adcetris is discontinued due to any adverse event, however, the investigator will continue to observe the patient after treatment discontinuation until the adverse event resolves or improves wherever possible, and then complete the case report form and submit it to the Takeda MR.

#### 7.5 Confirmation of all-case surveillance

After the completion of the study, the principal investigator will confirm that case report forms of all patients treated with Adcetris have been submitted, and sign or fill in his/her name with seal on All-Case Surveillance Confirmation Form and submit it to the Takeda MR.

#### 8.0 Estimated Study Period

Study period: Starts on the day of the launch of Adcetris (April, 2014) and ends once the all-case surveillance is no longer a condition for approval of the product.

Patient enrollment period: Starts on the day of the launch of Adcetris (April, 2014) and ends once the all-case surveillance is no longer a condition for approval of the product.

The expected number of enrolled patients (140) was achieved. Therefore, the study will move to the period only requiring patient enrollment (not requiring the completion and submission of case report forms).

After moving to the period only requiring patient enrollment, it may be required to complete and submit case report forms upon request by the regulatory authority.

#### 9.0 Outcome Measures

The investigator will record data listed below in both Patient Enrollment and Case Report Forms. Study schedule is provided in Appendix 1.

##### 9.1 Data to be recorded in Patient Enrollment Form

###### 1) Outcome measures

Name of the institution, name of the investigator completing Patient Enrollment Form,

expected date of the start of treatment with Adcetris, patient identification number, patient initial, sex, date of birth, diagnosis, performance status, CD30, past history of severe hypersensitivity to any ingredient of Adcetris, expected concomitant use of other antineoplastic drugs, and presence/absence of infections, peripheral nerve disorders, hepatic disorders, severe renal disorders, or pregnancy/breast-feeding

2) When to collect outcome measure data

At the time of patient enrollment

## 9.2 Data to be recorded in Case Report Form

### 9.2.1 Cover sheet of Case Report Form

Date of the final completion of Case Report Form and name of the investigator completing Case Report Form

### 9.2.2 Patient demographics and baseline characteristics

1) Outcome measures

Date of diagnosis of Hodgkin's or anaplastic large cell lymphoma, site of involvement, ALK (in patients with anaplastic large cell lymphoma), clinical stage, presence/absence of B symptoms, ECOG Performance Status, therapeutic category, (presence/absence and detail of) hypersensitivity disposition, viral test results, past history of and concurrent pulmonary disorders, past history of and concurrent malignant tumours, (presence/absence and detail of) concurrent illnesses [other than pulmonary disorders and malignant tumours], (presence/absence and detail of) past history [other than pulmonary disorders and malignant tumours], height, weight, smoking history, and (presence/absence and detail of) prior treatment for Hodgkin's lymphoma or anaplastic large cell lymphoma (including drug therapy, radiotherapy, and hematopoietic stem cell transplantation)

2) When to collect outcome measure data

At the start of treatment with Adcetris

### 9.2.3 Treatment given

1) Outcome measures

Treatment with Adcetris and premedication to prevent infusion reaction (dose, date of premedication, and reasons for premedication to prevent infusion reaction and its discontinuation), (use or non-use, type, and date of) post-baseline hematopoietic stem cell transplantation, (presence/absence, name, and duration of) drugs other than Adcetris used for the treatment of the primary disease, and (presence/absence, name, and duration of) drugs used for the prevention of infection

2) When to collect outcome measure data

From the start of treatment with Adcetris until the completion of 16 cycles (or upon discontinuation of treatment with Adcetris)

#### 9.2.4 Tests and assessments

##### 9.2.4.1 Laboratory tests

###### 1) Outcome measures

Red blood cell count, hemoglobin level, white blood cell count, neutrophil count, lymphocyte count, platelet count, total bilirubin, AST, ALT, LDH, BUN, and serum creatinine

###### 2) When to collect outcome measure data

At each test time point during the period from the start of treatment with Adcetris until the completion of 16 cycles (or upon discontinuation of treatment with Adcetris)

##### 9.2.4.2 Best response

###### 1) Outcome measures

The best response (CR, CRu [for patients with no PET scan data], PR, SD, or PD) will be assessed based on CT and PET scans of the neck, chest, abdomen, and pelvis according to the best response assessment criteria (see Appendix).

###### 2) When to collect outcome measure data

After 16 cycles of treatment with Adcetris (or upon discontinuation of treatment with Adcetris)

##### 9.2.4.3 Date of the final observation

###### 1) Outcome measures

Date of the final observation

###### 2) When to collect outcome measure data

After 16 cycles of treatment with Adcetris (or upon discontinuation of treatment with Adcetris)

##### 9.2.4.4 Other assessments

###### 1) Outcome measures

Pregnancy during the observation period (for females only)

If pregnancy is detected during the observation period, it should be reported to the Takeda MR immediately.

###### 2) When to collect outcome measure data

From the start of treatment with Adcetris until the completion of 16 cycles (or upon discontinuation of treatment with Adcetris)

##### 9.2.5 Adverse events

###### 1) Outcome measures

Presence/absence of adverse events (see Table 1), adverse event terms, date of onset, CTCAE grade (the worst one), seriousness and its reason (see Table 2), (presence/absence and detail of) action taken to Adcetris, (presence/absence and detail of) intervention for

adverse events, date of outcome, outcome, causal relationship with Adcetris\* (see Table 3), and changes in laboratory test values associated with adverse events over time

If the outcome is “not recovered/not resolved” or “unknown,” and the causal relationship with Adcetris is considered unevaluable, the event should be followed wherever possible.

\* If the event is considered not related to Adcetris, its rationale should be collected. If the causal relationship with Adcetris is considered unevaluable, its reason should be collected.

Note) Points to consider regarding adverse events

Worsening of the primary disease should not be regarded as an adverse event. However, abnormal worsening of the primary disease (e.g., worsening beyond the expected natural course of the disease) should be regarded as an adverse event.

Disease progression should be regarded as worsening of the primary disease rather than an adverse event. However, clinical or laboratory progression of an existing cancer (including new metastasis) that meets any of the criteria for the seriousness of adverse events (see Table 2) should be considered a serious adverse event.

## 2) Adverse events of particular interest

The events listed below are events of particular interest; detailed information on these events should be collected wherever possible if they are observed:

- Peripheral nerve disorders
- Infections
- Neutropenia
- Infusion reactions
- Pulmonary disorders

\* Rationale for the selection of adverse events of particular interest

Of important identified risks listed in Risk Management Plan, those listed above were selected as adverse events of particular interest based on the following rationales:

### a) Peripheral nerve disorders

Peripheral nerve disorders are frequently observed after treatment with Adcetris. If the event of peripheral nerve disorder becomes severe, it is difficult to continue treatment with Adcetris. It is important to control the onset of the event to allow for continuation of treatment (including dose reduction and restart of treatment after treatment interruption). Therefore, the profile of peripheral nerve disorders in Japanese patients as an adverse event of particular interest will be determined (i.e., information useful for continuation of treatment with Adcetris, including risk factors, commonly reported time to onset, outcomes, and the status of treatment with Adcetris, will be collected).

### b) Infections

It is expected that Adcetris is used in patients who are immunocompromised due to prior treatment or the prior disease or those who are complicated with infection, and the incidence of infections is likely to be high. Therefore, the profile of infections in Japanese

patients as an adverse event of particular interest (i.e., the incidence and temporal relationship with the onset of neutropenia/lymphopenia) will be determined.

#### c) Neutropenia

It is expected that Adcetris is used in patients with decreased neutrophil count due to prior treatment, which may increase the risk of infection and result in a high incidence of infection/severe infection. It is important to control the neutrophil count to allow for continuation of treatment (including dose reduction and restart of treatment after treatment interruption) in terms of the prevention of infection. Therefore, the profile of neutropenia in Japanese patients as an adverse event of particular interest will be determined (i.e., the status of treatment with Adcetris and neutrophil count control will be assessed and information useful for continuation of treatment with Adcetris will be collected).

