###### 2) When to collect outcome measure data

At each test time point during the period from the start of treatment with Adcetris until the completion of 16 cycles (or upon discontinuation of treatment with Adcetris)

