5.0 Safety Analysis

5.1 Occurrences of adverse events and adverse drug reactions/infections

5.1.1 Occurrence of adverse events

(1) Analysis sets to be used

Safety analysis set, safety analysis set (Hodgkin’s lymphoma), and safety analysis set (anaplastic large-cell lymphoma)

(2) Data to be analyzed

Data listed below will be analyzed.

For data entered in the field of “Adverse events: [1] Peripheral nerve disorders] in the case report form, MedDRA PT Code for peripheral sensory neuropathy, peripheral motor neuropathy, or peripheral neuropathy should be assigned, regardless of data entered in “Symptoms” field (see Section 1.2, the same applies hereinafter).

MedDRA PT Code for “Infusion related reaction” should be assigned to the field of “Adverse events: [4] Infusion reaction” in the case report form, regardless of data entered in “Symptoms” field (see Section 1.2, the same applies hereinafter).

Neutrophil count decreased (PT Code 10029366) will be replaced by Neutropenia (PT Code 10029354), Lymphocyte count decreased (PT Code 10025256) by Lymphopenia (PT Code 10025327), White blood cell count decreased (PT Code 10047942) by Leukopenia (PT Code 10024384), and Platelet count decreased (PT Code 10035528) by Thrombocytopenia (PT Code 10043554) (the same applies hereinafter).

Data item	Data to be analyzed
Number of patients with adverse events	Number of patients experiencing adverse events
Number of adverse events	Number of adverse events observed. If the same patient has multiple occurrences of the same adverse event (PT), the total number of occurrences will be calculated.
Percentage of patients with adverse events	Is calculated using the following formula: number of patients with adverse events/number of patients included in the safety analysis set × 100.
Type of adverse events	The incidence of adverse events will be calculated by SOC and PT. For SOC, the number and percentage of patients with adverse events will be calculated. For PT, the number and percentage of adverse events will be calculated. SOCs will be presented in the internationally agreed order, and PTs will be presented in ascending order of HLGT and PT codes if their SOCs are “Investigations,” and in ascending order of PT code otherwise. If the same patient has multiple occurrences of the same adverse event (PT), the event will be counted once per patient.

(3) Figure/table number

Tables 5.1-1 to 5.1.1-3

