The CTCAE grade (the worst one) is higher in the order of Grades 5, 4, 3, 2, 1, and unknown. If the same patient has multiple infections, the one with the highest CTCAE grade (the worst one) will be counted once for the category (the worst one).

Similar analyses will be performed for bacterial, fungal, and viral infections.

Data item	Category
CTCAE Grade (the worst one) of infection	None, Grade 1, Grade 2, Grade 3, Grade 4, Grade 5, or unknown

(3) Figure/table number

Tables 5.9.6-1 to 5.9.6-3

5.9.7 Occurrence of neutropenia considered related to Adcetris by patient demographics and baseline characteristics

(1) Analysis sets to be used

Safety analysis set, safety analysis set (Hodgkin’s lymphoma), and safety analysis set (anaplastic large-cell lymphoma)

(2) Data to be analyzed

For each data item of patient demographics and baseline characteristics, patients will be stratified into the categories below, and the incidence of neutropenia considered related to Adcetris will be calculated by CTCAE Grade (the worst one). The CTCAE grade (the worst one) is higher in the order of Grades 5, 4, 3, 2, 1, and unknown. If the same patient has multiple occurrences of neutropenia, the event with the highest CTCAE grade will be counted once.

Data item	Category
CTCAE Grade (the worst one) of neutropenia	Grade 1, Grade 2, Grade 3, Grade 4, Grade 5, or unknown

Items and categories of patient demographics and baseline characteristics

Data item	Category
Prior hematopoietic stem cell transplantation	Absent, present (autologous), present (homologous), present (autologous and homologous), or unknown

Degree of decreased neutrophil count at baseline	No decrease, Grade 1, Grade 2, Grade 3, Grade 4, or unknown
Drugs used for the prevention of infection	Absent or present
Specific drug(s) used for the prevention of infection	Antibiotics/synthetic antibacterial agents, antifungals, antivirals, trimethoprim-sulfamethoxazole combinations, or other

(3) Figure/table number

Tables 5.9.7-1 to 5.9.7-3

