Time of onset	
Is calculated using the following formula: date of onset of adverse events (or adverse drug reactions, etc.) – date of the initial dose of Adcetris + 1.
 
If the day, month, and year of onset of adverse events (or adverse drug reactions, etc.) are unknown, the time of onset should be handled as missing, and the category for the time of onset should be “unknown.”

Time to the worst grade	
Is calculated using the following formula: date of the worst CTCAE grade – date of the initial dose of Adcetris + 1.
 
If the day, month, and year of the worst CTCAE grade are unknown, the date of the worst CTCAE grade should be handled as missing, and the category for the date of the worst CTCAE grade should be “unknown.”

Infection	A concurrent illness or adverse event that falls under the category of MedDRA SOC Code 10021881 (Infections and infestations)
Grade 3 or 4 decreased neutrophil count	Neutrophil count <1,000/mm ³
Grade 3 or 4 decreased lymphocyte count	Lymphocyte count < 500/mm ³
Neutropenia	An adverse event equivalent to MedDRA PT Codes 10029366 (Neutrophil count decreased) and 10029354 (Neutropenia).
Lymphopenia	An adverse event equivalent to MedDRA PT Codes 10025256 (Lymphocyte count decreased) and 10025327 (Lymphopenia).

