1.2 Definition

Term	Definition										
This/the product	Refers to Adcetris for intravenous drip infusion in this Statistical Analysis Plan.										
SOC	MedDRA/J System Organ Class										
PT	MedDRA/J Preferred Term										
Safety analysis set	Fixed patients included in the safety analysis set										
Safety analysis set (Hodgkin's lymphoma)	Patients included in the safety analysis set whose diagnosis is Hodgkin's lymphoma										
Safety analysis set (anaplastic large-cell lymphoma)	Patients included in the safety analysis set whose diagnosis is anaplastic large-cell lymphoma										
Neutropenia	Events equivalent to MedDRA PT Codes 10029354 (Neutropenia) and 10016288 (Febrile neutropenia) will be collected and analyzed. Neutrophil count decreased (PT Code 10029366) will be replaced with Neutropenia (PT Code 10029354).										
Degree of decreased neutrophil count at baseline	
The neutrophil count at baseline will be classified as shown in the table below. If the neutrophil count at baseline is missing, the degree of decreased neutrophil count should be handled as missing:
 
  
 No decrease	$\geq 2,000 /\text{mm}^3$	
 
 Grade 1	$\geq 1,500$ to $< 2,000 /\text{mm}^3$	
 
 Grade 2	$\geq 1,000$ to $< 1,500 /\text{mm}^3$	
 
 Grade 3	≥ 500 to $< 1,000 /\text{mm}^3$	
 
 Grade 4	$< 500 /\text{mm}^3$	
  
	No decrease	$\geq 2,000 /\text{mm}^3$	Grade 1	$\geq 1,500$ to $< 2,000 /\text{mm}^3$	Grade 2	$\geq 1,000$ to $< 1,500 /\text{mm}^3$	Grade 3	≥ 500 to $< 1,000 /\text{mm}^3$	Grade 4	$< 500 /\text{mm}^3$
No decrease	$\geq 2,000 /\text{mm}^3$										
Grade 1	$\geq 1,500$ to $< 2,000 /\text{mm}^3$										
Grade 2	$\geq 1,000$ to $< 1,500 /\text{mm}^3$										
Grade 3	≥ 500 to $< 1,000 /\text{mm}^3$										
Grade 4	$< 500 /\text{mm}^3$										
Antibiotics/synthetic antibacterial agents	Drugs with the first three digits of YJ Code being either one of 611 to 616, 619, or 624 that are entered in the field of "Drugs used for the prevention of infection" (If more than one antibiotics/synthetic antibacterial agents are used in the same patient, it will be counted as one patient.)										

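### Neutropenia incidence and grade are tabulated only from reported adverse events, so Grade 3 or 4 neutrophil counts without an event entry are not counted, though the counts are collected

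*Protocol*

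**What the plan says.** **Collected.** Protocol 9.2.4.1 lists the tests on the case report form: "Red blood cell count, hemoglobin level, white blood cell count, neutrophil count, lymphocyte count, platelet count" and several chemistry values. They are recorded "At each test time point during the period from the start of treatment with Adcetris until the completion of 16 cycles", or until discontinuation. Under Protocol 9.2.5, neutropenia is one of five events of particular interest, and its stated profile is that "the status of treatment with Adcetris and neutrophil count control will be assessed".

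**Analysed as events.** SAP 5.9.7, in the version written for the final analysis, states that "the incidence of neutropenia considered related to Adcetris will be calculated by CTCAE Grade (the worst one"). The worst CTCAE grade is an adverse event field under Protocol 9.2.5. Supplemental SAP 2 repeats the table in its section 2.1.1 and defines cases by coded terms: "Events equivalent to MedDRA PT Codes 10029354 (Neutropenia) and 10016288 (Febrile neutropenia) will be collected and analyzed". SAP 5.1.1 adds that "Neutrophil count decreased (PT Code 10029366) will be replaced by Neutropenia (PT Code 10029354"), which merges two reported terms and brings in no laboratory value. SAP 5.1.1, 5.2.1 and 5.2.2 tabulate all adverse events by preferred term whatever the causality, and 5.2.2 splits them at Grade 3.

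**Analysed as counts.** SAP 5.8.1 gives summary statistics and box plots of the neutrophil count at baseline and after each of cycles 1 to 15. Supplemental SAP 1 section 1.2 has two separate entries. One is an event definition of neutropenia ("An adverse event equivalent to MedDRA PT Codes 10029366 (Neutrophil count decreased) and 10029354 (Neutropenia")). The other is "Grade 3 or 4 decreased neutrophil count", defined as a count below 1,000/mm3. Section 2.2.1 of that supplement joins the two to form the set for the analysis of infections within 7 days.

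**The concern.** Whether a low count becomes an adverse event depends on the investigator entering it. The plan holds the counts themselves but never asks how many patients fell below 1,000 or 500/mm3 at any time. Such a patient without an entry does not appear in any neutropenia row, yet remains in the safety analysis set that forms the denominator. The omission can only lower the reported incidence.

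Grade 3 or higher neutropenia is one of the five rates quoted in the enrollment rationale (Protocol 3.2), so readers will compare the result with it. The plan also differs within itself. Supplemental SAP 1 accepts that a low count may stand apart from a neutropenia event and uses it to select patients. The incidence tables do not, and no table reconciles the two groups.

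**Working it through.** **1. Does any table count the laboratory cases?**

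| Place | Source | Shows patients with a count <1,000/mm3 and no event? |
|---|---|---|
| SAP 5.1.1, 5.2.1, 5.2.2 | all reported events | no |
| SAP 5.9.7; Suppl. SAP 2, 2.1.1 | reported events considered related | no |
| SAP 5.8.1 | counts, one per cycle | no |
| Suppl. SAP 1, 2.2.1 | events or counts <1,000/mm3 | only mixed with event cases, to define the infection set |

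SAP 5.8.1 does not fill the gap, for three reasons. Its minimum and percentiles at a time point do not give the number of patients ever below a cut-off. SAP 1.4 keeps the value closest to the next dose date, so a mid-cycle low can be passed over; after cycle 1 the acceptable window is a single date. The series also ends after cycle 15.

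**2. The plan's own figure (Protocol 3.2).** With the exact binomial tail, P(X >= 10 | n = 140, p = 0.11) = 0.952, and 0.949 at n = 139, so 140 is the smallest sufficient number. P(X >= 4 | 140, 0.06) = 0.971. The enrollment figure reproduces. Infusion reactions drive it, so the source of neutropenia cases does not change it.

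**3. Illustrative size.** Inputs: 20% for Grade 3 or higher and 140 patients (Protocol 3.2), giving 0.20 × 140 = 28. Let u be the share of patients with a Grade 3 or 4 count but no event entry. The documents give no value, so u = 0.2 to 0.4 is an assumption. Protocol 3.2 does not say whether the 20% is event-based or laboratory-based, so both readings are shown, taking event cases as a subset of laboratory cases.

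| Reading of the 20% | Formula | u = 0.2 | u = 0.4 |
|---|---|---|---|
| true laboratory rate; event table shows | 28 × (1 − u) | 22.4 (16.0%) | 16.8 (12.0%) |
| event rate; laboratory rate is | 28 / (1 − u) | 35 (25.0%) | 46.7 (33.3%) |

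Over a wider range on the first reading, u = 0.10, 0.25 and 0.50 give 25, 21 and 14 patients: 17.9%, 15.0% and 10.0%. The exact (Clopper-Pearson) 95% intervals are 11.9% to 25.2%, 9.5% to 22.0% and 5.6% to 16.2%. The interval still contains 20% at u = 0.25 and no longer does at u = 0.50.

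**The case against.** The best defence is that the event-based analysis is coherent and does what the protocol asks. Protocol 10.4.1 promises adverse event frequencies and 10.4.3 promises only summary statistics of laboratory values. The SAP delivers both, with actions taken, outcomes by action and a patient listing for neutropenia. The adverse event definition in Protocol Table 1 covers abnormal laboratory findings, and neutropenia is a named event of interest, so many low counts should be entered. All of this stands, and it means that no protocol commitment is broken. It does not show the gap to be empty, because no planned output compares counts with entries.

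Several stronger readings are tempting, and the documents do not support them:

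- A reader might infer that incidence will come out at 12% to 16%. That needs both an assumed non-reporting rate and a laboratory reading of the 20%, and neither is given.
- A reader might infer that only related events are ever counted. SAP 5.1.1, 5.2.1 and 5.2.2 cover all causes, and the SAP's definition of adverse drug reactions drops only events judged not related.
- A reader might infer that laboratory-defined cases are ignored throughout. They can enter the combined set in Supplemental SAP 1 section 2.2.1. However, they are not separated there, and that set is limited to falls considered related to the drug, while no causality field for a bare count is described.
- A reader might infer that reporting varies by site, or is poorer in patients who start with low counts. Either is plausible; neither is shown.

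**Conclusion.** The concern holds as a gap in the analysis that is cheap to close. It is not an error in the tables that are planned. All incidence and grade tables for neutropenia depend on event entry, and the collected counts are never reduced to a worst grade per patient. For overall Grade 3 or 4 incidence the direction is certain, since missing cases can only lower it; the size is unknown. The only figures available are conditional. With 20% to 40% of such patients lacking an entry, the event table would read 16% to 12% against a true laboratory 20%, or the laboratory rate would be 25% to 33% against an event-based 20%. Enrollment of 140 is untouched.

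**What to change.** Add one table beside SAP 5.9.7 and Supplemental SAP 2 section 2.1.1. For each patient in the safety analysis set, take the lowest post-baseline neutrophil count over all collected tests, not only the one kept per cycle. Grade it by the cut-offs that the SAP already applies at baseline (2,000, 1,500, 1,000 and 500/mm3) and cross-tabulate it with baseline degree. State the number of patients with a Grade 3 or 4 count but no reported neutropenia event. Keep the event-based tables as they are.

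The cost is one table from data and cut-offs already in the plan. Two limits should be stated with it. The table includes falls from other causes. It also depends on how often each site tests, because the protocol sets no testing frequency, so the number of tests per patient should be shown alongside.
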